9 INVESTIGATIONAL PLAN

9.1 Overall Study Design and Plan: Description

This is an open, single-center phase I dose escalation trial in 24 healthy subjects of both sexes. Subjects will be allocated to two different dose cohorts each receiving two vaccine injections, one at day 0 and another on day 28. For safety reasons, subjects will be vaccinated in both cohorts in a staggered manner. Dosing of subjects will commence in dosing cohort 1 (1×10^7 pfu) followed by dosing cohort 2 (1×10^8 pfu). Dosing of cohort 2 will not start before both vaccinations and safety assessments of the first dose cohort are completed.

Second immunization and dose escalation will be performed following a review of the interim safety report by the Local Safety Board.

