9.3.3.3 Criteria for Termination of the Study (Holding Rules)

Safety holding rules will apply throughout the entire study period. Further injections will be discussed with the Local Safety Board. Should a holding rule be activated, the PI will inform the sponsor. The sponsor has to inform the competent authorities and the ethics committee within 15 days.

If the event(s) occur in the higher-dose cohort, the follow-up phase of the lower dose cohort will continue. The discontinuation of a holding rule should be communicated to all entities in the same manner and timeframe as described above.

The Local Safety Board review will consider:

- The relationship of the AE or SAE to the vaccine
- The relationship of the AE or SAE to the vaccine dose, or other possible causes of the event
- If appropriate, additional screening or laboratory testing for other subjects to identify those who may develop similar symptoms, and alterations to the current informed consent form will be discussed

All injected subjects will be followed for safety until resolution or stabilization (if determined to be chronic sequelae) of their AE. AE grading will be done according to FDA's 2007 voluntary guidance: (14) or according to CTCAE v4 (15). Please refer to Table 3- Table 5 for further details.

The holding rules are as follow:

- Solicited (expected) local adverse events:
 - If more than 25% of injections (minimum 2 individuals) are followed by Grade 3 solicited swelling or pain or Grade 4 redness beginning within 3 days after injection (day of injection and one subsequent day) and persisting at Grade 3 (swelling or pain)/4 (redness) for >48 – 72 hours
- Solicited (expected) systemic adverse events:
 - If more than 25% of injections (minimum 2 individuals) are followed by Grade 3 solicited systemic AE (or Grade ≥ 3 physical observations as defined above and in Section 9.7.11) beginning within 3 days after study injection (day of injection and one subsequent day) and persisting at Grade ≥ 3 for >48 – 72 hours
- Unsolicited (unexpected) adverse events:
 - If more than 25% of subjects (minimum of 2 individuals) develop a Grade ≥ 3 unsolicited AE (including laboratory AE and physical observations) that is considered probably or definitely related to injection and persists at Grade 3 for >48 – 72 hours
- A serious adverse event occurs that may be related to the IMP

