9.4 Treatments

9.4.1 Treatments Administered

All eligible subjects will be allocated to one of the two dose cohorts according to the assignment list. Each subject will receive two or three vaccine injections administered as i.m. injections in the deltoid region of the upper arm muscle.

For safety reasons dose administration in each dose level will be performed in four groups. Dose administration for the first subject at all dose levels will be vaccinated 48 hours prior to the second groups (second and third subject) of this dose level. The second and the third subject will be vaccinated in an interval of at least 5 min and after a period of at least 48 hours after the first subject to assess for immediate hypersensitivity reaction (within 60 min after the vaccination) or cytokine release (within 24 hours following the vaccination). The next group of four subjects can be vaccinated in parallel (in intervals of at least 5 min) at least 24 hours after the second group and at least 24 hours before the last group. The last group of the dose cohort including five subjects will be dosed on the same day in intervals of at least 5 min. Dosing events are supervised by an Investigator.

Figure 1: Dose administration groups

A Local Safety Board will be established for this study. Planned 2nd immunization and dose escalation will occur following a review of the interim safety report. Interim safety reports will contain safety data obtained until day 7.

The second immunization for each subject will be done after the Local Safety Board reviewed individual safety data of the respective subject.

All subjects who consented to the study extension will be immunized a third time with a vaccine dose of 1×10^8 pfu MVA-MERS-S at 12 months (± 4 months) after the first vaccination.

For the decision about dose escalation safety data obtained until day 7 after the second immunization of all subjects of the first cohort will be taken into account.

A dose level may be repeated and furthermore, additional dose step(s) may be added but not exceeding dose of 1×10^8 pfu MVA-MERS. The decision to repeat and/or to modify the dose level and/or to add additional dose steps will be taken by the Local Safety Board and the Ethics Committee and Competent Authority will be notified.

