9.10 Local Safety Board

During the trial, the Local Safety Board will review and judge the safety, tolerability, after each dose-step and prior to the next dose-step of the trial. Based on these data the Local Safety Board will/may decide

- Whether there will be a next dose cohort and if the planned dose for the next dose cohort has to be reduced.
- Whether there will be added additional dose step(s) or dose step(s) will be repeated.

Evaluation will take the results of the pre-clinical studies and the ongoing phase I studies in prior mentioned other countries into account.

An interim safety report, summarizing the safety (AEs, vital signs, 12-lead ECGs, and laboratory safety data) will be prepared and reviewed by the Principal Investigator and Medical Monitor before the second immunization for each dose cohort.

Planned dose escalation will occur after the second immunization of all subjects of the 1st dose group following a review of the interim safety report summarizing the safety (AEs, vital signs, 12-lead ECGs, and laboratory safety data) and any available immunological data by the Principal Investigator and Medical Monitor.

The dose for the next escalation step may be reduced if there are concerns about the safety. A dose level may be repeated and furthermore, additional dose step(s) may be added but not exceeding dose of 1×10^8 pfu MVA-MERS. The decision to repeat and/or to modify the dose level and/or to add additional dose steps will be taken by the Local Safety Board.

In addition, a Local Safety Board meeting will be conducted whenever safety relevant data occur that might have an influence on the trial.

Members of the Local Safety Board will be the medical monitor, as well as the Principal Investigator, or at least one of the deputies and a representative of the sponsor.

At a minimum the holding rules (criteria for termination of the study) specified in the protocol will automatically apply (if activated) for not proceeding with a higher dose.

The decisions of the Local Safety Board meeting will be briefly summarized by CTC North and signed by all members involved in the meeting and the decision. The summarized safety report of each Local Safety Board Meeting will be submitted to the competent national authority (Paul-Ehrlich-Institute) and the independent ethics committee (Ethik-Kommission der Ärztekammer Hamburg) for notification.

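### Section 9.4.1 requires Local Safety Board review of each subject's own data before dose 2, but schedules none before the 10^8 pfu third dose

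*Protocol*

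**What the plan says.** Section 9.4.1 sets an individual condition on the second injection: "The second immunization for each subject will be done after the Local Safety Board reviewed individual safety data of the respective subject". The statement that follows, on the third injection, reads "All subjects who consented to the study extension will be immunized a third time with a vaccine dose of" 10^8 pfu, at 12 months (± 4 months) after the first. It carries no individual review.

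The other sections on scheduled review do not name the third injection either:

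- Section 9.1: "Second immunization and dose escalation will be performed following a review of the interim safety report by the Local Safety Board".
- Section 9.4.1, on escalation, uses "For the decision about dose escalation safety data obtained until day 7 after the second immunization of all subjects of the first cohort".
- Section 9.10 has the Board judge safety "after each dose-step and prior to the next dose-step of the trial" and places the interim safety report before the second immunization of each cohort and before escalation. The decisions it lists concern cohorts and dose steps, for example "Whether there will be a next dose cohort and if the planned dose for the next dose cohort has to be reduced".

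Two general provisions do reach the third injection. Section 9.3.3.3 says "Further injections will be discussed with the Local Safety Board", and section 9.10 adds that "a Local Safety Board meeting will be conducted whenever safety relevant data occur that might have an influence on the trial".

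**The concern.** The individual check is attached to the step that carries less new exposure. Dose 2 repeats the dose the subject has already had. For cohort 1, dose 3 is the subject's first exposure to 10^8 pfu. In a first-in-human trial one would expect at least the same individual check before the larger step.

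At stake is a single subject with a notable but non-serious finding after dose 2, such as a Grade 3 reaction or a troponin rise. Section 7.4.1.4 names myo-/pericarditis among the potential risks, and troponin and ECG are collected after dose 2. As written, that subject could go on to 10^8 pfu on the investigator's eligibility decision, without the Board being required to look at the profile.

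**Working it through.** The protocol gives no figure to reproduce here. The check sets the safeguards beside one another and counts the data concerned.

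**Dose step.** Cohort 1 receives 10^7, 10^7 and then 10^8 pfu (Synopsis). Dose 2 / dose 1 = 1; dose 3 / dose 2 = 10^8/10^7 = 10. Cohort 2 stays at 10^8 throughout, a ratio of 1.

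**Data collected after the last scheduled individual Board review.** That review comes before dose 2 on day 28. Counts are from Table 1a. Day-28 samples are left out because their timing relative to the injection is not used here.

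| Data | Days after dose 2 | Count | Of these, after day 35 |
|---|---|---|---|
| Adverse events | 29, 35, 42, 56, 84, 180 | 6 | 4 |
| Safety bloods | 29, 35, 42, 180 | 4 | 2 |
| Troponin T | 35, 42, 180 | 3 | 2 |
| ECG | 35, 42 | 2 | 1 |

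The last column applies to cohort 1. Under section 9.4.1 the escalation review uses data to day 28 + 7 = 35, and it is a cohort-level review. For cohort 2 no escalation review follows, because 10^8 pfu is the ceiling, unless the dose-step wording of 9.10 is read to cover the boost.

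**What each general safeguard requires for one subject before dose 3.**

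- *Holding rules (9.3.3.3).* They apply throughout. Apart from the rule on a possibly related serious event, each needs more than 25% of injections or subjects and at least 2 individuals. One subject of 12 is 1/12 = 8.3%, so a single non-serious case cannot activate them.
- *Discussion of further injections (9.3.3.3).* It covers dose 3, but sets no data cut-off, time point or subject-level content.
- *Event-driven Board meeting (9.10).* It depends on someone first judging the data relevant to the trial.
- *Board-recommended withdrawal (9.3.3.1).* It is a power of the Board and does not require a review.
- *Eligibility check at the boost visit (9.4.10.3.5).* The criteria added for dose 3 in 9.3.1 and 9.3.2 concern contraception, pregnancy and other vaccines. None refers to reactions to doses 1 or 2. General exclusion 24 could catch such a case, but it rests on the investigator's opinion.
- *Physician review of adverse events and laboratory values (9.5.2.8, 9.5.2.8.11).* All these data are seen by a physician, but this is not Board review.

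**Time available.** The latest day-180 visit is day 180 + 7 = 187. The earliest boost is month 8, about 8 × 365/12 = 243 days. That leaves about 243 − 187 = 56 days for a review.

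**The case against.** The best case against is that the Board is already involved. Section 9.3.3.3 says without exception that further injections will be discussed with it, and dose 3 is a further injection. The Board consists of the medical monitor, the principal investigator or a deputy, and a sponsor representative. Serious events go to the medical monitor, and an investigator decides eligibility after a history update, physical examination and ECG at the boost visit. Much individual information therefore reaches Board members or their delegates anyway.

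The asymmetry can also be defended. Dose 2 comes 28 days after a first-in-human exposure, whereas dose 3 comes 8 to 16 months after dose 1, with a day-180 visit in the planned schedule. If the sequence ran as planned, cohort 2 would normally have received 10^8 pfu before cohort 1 was boosted, although the protocol gives no dates.

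Most of this stands, and it limits the weight of the point. It does not remove the point. The protocol did not rely on the general discussion alone for dose 2, and that discussion has no subject-level content for dose 3. The gain from an individual review is that the medical monitor and the sponsor representative would see the profile as well as the investigator.

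A reader might go further and infer that no safety oversight precedes dose 3. The safeguards above contradict that. Nor would ineligible subjects be boosted because 9.4.1 names consent alone: the Synopsis requires eligibility, 9.3.1 and 9.3.2 give criteria, and 9.4.10.3.5 has the check, so that omission is editorial. A third inference is that 9.4.1 orders 10^8 pfu even if the Board had found that dose unwarranted. This matters only if the Board had declined the dose, which the protocol does not say, and the Board keeps its power over dose levels under 9.4.1 and 9.10.

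**Conclusion.** The point holds in a narrow form. The protocol schedules an individual Board review before dose 2 and no corresponding one before dose 3, although dose 3 is ten times the earlier dose for up to 12 subjects (cohort 1). Up to 12 more in cohort 2 receive dose 3 at an unchanged dose, so at most 24 subjects are concerned. The weight is minor: it is an inexpensive safety improvement, and no endpoint, estimate or analysis changes.

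The conclusion rests on three readings:

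- The sentence on further injections in 9.3.3.3 does not itself require a subject-by-subject review.
- The dose-step review in 9.10 is cohort-level, as its listed decisions suggest.
- The day-35 cut-off in 9.4.1 governs the escalation review. Section 9.1 also asks for completed safety assessments in cohort 1 and could be read more widely. That would change the last column of the table, but not the absence of an individual review.

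A Board procedure kept outside the protocol could already provide for this review.

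**What to change.** In section 9.4.1, change the opening of the sentence on individual Board review so that it covers *the second and, where applicable, third immunization* of each subject, and leave the rest of the sentence as it is. The review would use the data already collected through day 180.

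The cost is one wording change and Board time for at most 12 + 12 = 24 existing profiles. No visit, sample or new committee is needed.

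While the section is open, the boost sentence can be tidied to name eligibility as well as consent, in line with the Synopsis. That is an editorial correction and separate from this point.

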9.4.2 Identity of Investigational Medicinal Product

Name:	MVA-MERS-S
Dosage form:	Suspension for injection in a pre-filled syringe
Active substances:	MVA-MERS-S
Route:	IM injections
MAH:	Ludwig-Maximilians-Universität München

Additional information can be found in the Investigator's Brochure [13].

9.4.2.1 Labeling

The study vaccine will be provided by IDT Biologika GmbH, Dessau to CTC North, and will be labeled in accordance with § 5 GCP-V.

9.4.2.2 Packaging

Sponsor will provide study vaccine for this study. Investigational medicinal product will be provided in glass vials. These containers are suitable for the purpose and ensure the stability of the investigational medicinal product.

9.4.2.3 Storage

The investigator has overall responsibility for ensuring that study medication is stored under appropriate conditions in a secure, limited-access location. Study medication is distributed by a nominated member of the study team.

Study medication must be stored in accordance with labeled storage conditions ($\leq -20^{\circ}\text{C}$). Temperature monitoring is required at the storage location to ensure that the study medication is maintained within an established temperature range. The temperature is monitored such that at least minimum and maximum temperature values throughout the total duration of the study are recorded and records are maintained.

The sponsor must be notified of any excursion from the established range. Relevant temperature excursions will require site investigation as to cause and remediation. The sponsor will determine the ultimate impact of excursions on the investigational medicinal product and will provide supportive documentation as necessary.

9.4.2.4 Shipment

The investigational medicinal products will be provided by the sponsor in sufficient quantity. The address for delivery purposes is:

CTC North GmbH & Co. KG
am Universitätsklinikum Hamburg-Eppendorf
[name], Germany

The batch number of the IMP used in the study will be given in the study report.

9.4.2.5 Drug Accountability

The PI has the overall responsibility for administering the investigational medicinal products. The IMP must be administered in the manner specified in the study protocol and the pharmacy manual.

The PI or an authorized member of the study team will acknowledge receipt of the study medication documenting shipment content and condition. Damaged supplies will be replaced. Accurate records of all study medication received, dispensed, used, returned or destroyed must be maintained. No study medication may be destroyed or returned from the investigational site without prior knowledge and written consent by the sponsor. If such transfer is authorized by the sponsor, all applicable local, state and national laws must be adhered to for the transfer.

An Investigator will administer the investigational medicinal products. All administrations will be documented in the site's drug accountability log or other study drug record.

The sponsor or its representatives must be permitted access to review the supplies storage and distribution procedures and records.

At the end of the study or as instructed by the sponsor all unused stock and empty used boxes are sent to a nominated contractor or will be destroyed on behalf of the sponsor. Study medication being returned or destroyed must be counted and verified by clinical investigational site personnel and the sponsor or designee. All certificates of delivery/drug receipts should be signed by the site representative to confirm contents of shipment. Shipment return forms must be signed prior to shipment by CTC North. The sponsor must give authorization to return or destroy any study medication prior to shipment or destruction. Shipment of all returned study medication must comply with local, state, and national laws.

Based on the entries in the site drug accountability logs, it must be possible to reconcile study medication delivered with those used and returned. One hundred percent of the study medication must be accounted for and all discrepancies investigated and documented.

9.4.2.6 Subject Compliance

For study medication administration at CTC North, compliance must be assessed by observation of dosing. Details will be recorded on the drug accountability log or other appropriate source documents.

9.4.3 Preparation and Administration

Study medication will be provided in glass vials for administration with conventional syringes. Instructions for storage, preparation, administration, and destruction of study medication are presented in the pharmacy manual.

The vaccine will be injected intramuscularly into the deltoid region of the upper arm muscle.

The vaccine must not be administered to subjects allergic to the active substance, to any of the excipients, to eggs, chicken proteins, and gentamycin or with a history of life-threatening reactions to the study vaccine containing the same substances. Vaccine must not be administered to subjects with febrile illness or acute infection.

The study personnel must clean the site on injection with a suitable antiseptical and let the antiseptical evaporate before vaccination.

Subjects must be kept under observation by authorized members of the study team for 24 hours after vaccination to ensure their safety. Any reactions reported during observation period will be documented.

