Ambulatory Visit		√	√	√	√	√	√
Dosing		√ _i					
Injection site & systemic events/ reactions assessment		√ _d	√	√	√	√	√
Temperature		√ _d	√	√	√	√	√
Alcohol Breath Test		√ _f					
Training/ Dispensing subject diary		√					
Review/ Collection of subject diary			√	√	√	√	√
Adverse Events & Concomitant medication		√ _d	√	√	√	√	√
Phone call	√						
Laboratory Analysis							
Phase of study	Phone Call	Dosing	Ambulatory Visits				End of Study
Study day		0	1	3	7	14 (±2)	28(±2)
Troponin T		√					√
Safety Lab blood (Clinical Chemistry, Hematology)		√	√	√	√	√	√
Safety Lab Urine		√			√	√	√
Urine Drug Screen		√					
Pregnancy Test		√ _{fh}					√ _h
Anti-MVA-MERS Elisa		√			√	√	√
Neutralization Assay		√			√	√	√
T-cell response		√			√	√	√
RNA blood sample storage		√	√	√	√		

Innate immunity		√	√	√	√		
PBMC freezing and plasma aliquots		√	√	√	√	√	√

^a Symptom-targeted physical examination

^b Please refer to Table for frequency of vital signs examinations

^c Only weight

^d Please refer to Table for frequency of Adverse Events and Concomitant Medication questioning.

^e Morning check-out

^f Before immunization

^g Serum pregnancy test

^h Urine pregnancy test

ⁱ Subjects will be monitored and evaluated for AEs for at least 30 minutes after vaccination in attendance of an investigator

Table 2a: Detailed Time and Events

Study Day	Time after Dose administration (hours)	Dosing	Vital Signs	Temperature	Adverse Events/ Con Med	Injection site/ systemic reaction/ Events assessment
0	0 ¹	√	√	√	√	
0	2		√	√	√	√
0	4		√	√	√	√
0	6		√	√	√	√
0	8		√	√	√	√
0	12		√	√	√	√
1	24		√	√	√	√
28	0 ¹	√	√	√	√	√
28	2		√	√	√	√
28	4		√	√	√	√
28	6		√	√	√	√
28	8		√	√	√	√
28	12		√	√	√	√
29	24		√	√	√	√

¹ Events must be completed before dose administration

Table 2b: Detailed Time and Events for 3rd vaccination

Study Day	Time after Dose administration (hours)	Dosing	Vital Signs	Temperature	Adverse Events/ Con Med	Injection site/ systemic reaction/ Events assessment
0	0 ¹	√	√	√	√	
0	2		√	√	√	√
0	4		√	√	√	√
0	6		√	√	√	√

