7.4.1.2 Administration of IMP (Study Vaccine)

Serious allergic reactions including anaphylaxis may occur and for this reason subjects will be inoculated in a clinical area where Advanced Life Support trained physicians, equipment and drugs are im-

mediately available for the management of any serious adverse reactions. Participants will be observed for 24 h after vaccination. Subjects will be monitored and evaluated for AEs for at least 30 minutes after vaccination in attendance of an investigator.

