7.4.1.4 Summary of Potential Risks for Study Participants

In summary, preclinical data suggest a favorable safety and tolerability profile. An extensive body of relevant preclinical studies have been conducted that are needed to proceed to Phase I clinical testing. Although potential risks are known, such as Myo-/pericarditis, Vaccinia rash, eczema vaccinatum, Post-vaccinial encephalitis, so far clinical trials on MVA have reported transient and spontaneously resolved adverse events and no serious ones. Based on available information and the design of the study, the sponsor and the PI consider the trial to be ethically acceptable. The duration of confinement, the medical surveillance and the chosen time intervals for the sequential dosing of the first, second and third subjects of each dosing cohort are considered adequate to ensure maximal safety of the subjects and have been established with guidance of the competent authority. Thus, taking into account the safety measures to minimize risks for study participants, the exposure of healthy subjects with MVA-MERS-S vaccine is justified since the potential risks and disadvantages for study participants are outweighed by the potential benefits for medical research, medical practice and eventually for individuals at risk of MERS.

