9.4.10.3 Screening, Confinement and Ambulatory Visits

9.4.10.3.1 Confinement (Day -1 to Day 1 and Day 27 to Day 29)

The Subjects will be admitted to the study ward in the evening on Day -1 going through regular check-in procedures including an ID check, vital signs, an inclusion/exclusion check, an alcohol breath test and a urine drug, and pregnancy test. The Subjects will stay on the ward until the morning of Day 1 experiencing blood draws for immunogenicity analysis, documentation of occurrence of any injection site reaction, systemic events/reaction and adverse event questioning throughout the confinement period. Subjects will be dismissed at the earliest after the 24 h after vaccination and after subjects were trained on the use of the diary.

This schedule will be repeated in for the second vaccination on day 27 to day 29.

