9.4.10.3.4 Ambulatory Visits

Subjects will return to the study ward for ambulatory visits on study day 3, 7 and 14 (± 2), after the first vaccination and on study day 35, 42 (± 2), 56 (± 3), 84 (± 3) after the second vaccination. On the ambulatory visits the following events will be performed:

- Targeted Physical Examination (only on day 42)
- Vital signs/ Temperature
- 12-lead ECG (only on day 7, 14, 35, 42)
- Injection Site reaction & systemic events/ reaction assessment (only on day 3, 7, 14, 35 and 42)
- Safety Laboratory (Urine) (only on day 7, 14, 35, 42)
- Safety Laboratory (Blood) (only on day 3, 7, 14, 35, 42)
- Blood sampling for troponin (only on day 7, 14, 35, 42)
- Blood sampling for humoral immunogenicity (only on day 7, 14, 35, 42, 56, 84)
- Blood sampling for cellular response (only on day 14, 42, 56, 84)
- PBMC freezing and plasma aliquots
- Blood sampling for RNA storage (only on day 3, 7, 35)
- Blood sampling for innate immunity (only on day 3, 7, 35)
- Adverse events assessment
- Concomitant medication assessment
- Collection and review of diary

9.4.10.3.5 Ambulatory vaccination and subsequent ambulatory visits (only for subjects who gave consent to the study extension)

Subjects will return to the study ward for an ambulatory vaccination visit 12 months (± 4 months) after the first immunization.

The following interventions will be performed:

- Informed Consent
- I/E Criteria check
- Update medical history
- Weight
- Physical examination
- Vital signs / Temperature
- 12-lead ECG
- Injection Site reaction & systemic events/reaction assessment
- AE/ConMed
- Alcohol Breath Test
- Urine Drug Screen
- Urine Pregnancy Test
- Safety Laboratory (Urine/Blood)
- Blood sampling for humoral immunogenicity
- Blood sampling for cellular response
- PBMC freezing and plasma aliquots
- Blood sampling for RNA storage
- Blood sampling for troponin
- Blood sampling for innate immunity
- Dosing
- Training on subject diary

After dosing the following events will be performed **at 2 h, 4 h and 6 h**:

- Vital signs (and at 0 h, before dose administration)
- Temperature (and at 0 h, before dose administration)
- (AE)/ConMed (and at 0 h, before dose administration)
- Injection site reactions & systemic events/reactions assessment

Subjects will return to the study ward for ambulatory visits on study day 1, 3, 7 and 14 (± 2), after the third vaccination.

On the ambulatory visits the following events will be performed:

- Vital signs/ Temperature

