9.4.10.3.6 End of study/ Early termination visit

An end-of-study follow-up visit will be performed on day 180 (± 7). The following interventions will be performed:

- Physical examination
- Vital signs/Temperature
- Weight
- AE/ConMed
- Urine pregnancy test
- Safety Laboratory (Urine and Blood)
- Blood sampling for Troponin T
- Injection site reactions & systemic events/reactions assessment
- Collection subject diary
- Blood sampling for humoral immunogenicity
- Blood sampling for cellular response
- PBMC freezing and plasma aliquots

For subjects receiving 3 vaccinations, an additional end-of-study visit will be 28 (± 2 days) after the 3rd vaccination. The following interventions will be performed:

- Vital signs/Temperature
- AE/ConMed
- 12-lead ECG
- Urine pregnancy test
- Safety laboratory (urine and blood)
- Blood sampling for Troponin T
- Injection site reactions & systemic events/reactions assessment
- Collection of subject diary
- Blood sampling for humoral immunogenicity
- Blood sampling for cellular response
- PBMC freezing and plasma aliquots

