9.5.3.5.4 ECG

The results of the 12 lead ECG will be listed by sampling times (screening and follow up) according to the data reported in the source documents.

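### Third-dose monitoring contradicts itself twice: 24-hour observation against an ambulatory visit last checked at 6 h, and a day-28 ECG in the text but not in the boost schedule table

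*Protocol*

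**What the plan says.** **Observation after vaccination.** Two general sections set a 24-hour period and do not distinguish between doses. Section 9.4.3: "Subjects must be kept under observation by authorized members of the study team for 24 hours after vaccination to ensure their safety". Section 7.4.1.2: "Participants will be observed for 24 h after vaccination". For doses 1 and 2 this is carried out through confinement (section 9.4.10.3.1): "Subjects will be dismissed at the earliest after the 24 h after vaccination". For the third dose, section 9.4.10.3.5 says: "Subjects will return to the study ward for an ambulatory vaccination visit 12 months" (± 4 months) after the first immunization. That section sets post-dose checks at 2, 4 and 6 h and a return on day 1. The detailed time-and-events table for the third vaccination shows the same hours.

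**ECG after the boost.** Section 9.4.10.3.6 begins its second list with "For subjects receiving 3 vaccinations, an additional end-of-study visit will be" 28 days (± 2) after that dose, and the list contains a 12-lead ECG. The boost schedule table has a single ECG tick, in the dosing column, with the footnote that places it before immunization. Its day-28 column has no ECG. Section 9.5.2.4 says ECGs are done at the times in Table 1.

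**Why ECG is collected.** Section 9.5.3.5 names the 12-lead ECG as a safety variable. Section 7.4.1.4 says: "Although potential risks are known, such as Myo-/pericarditis", followed by other vaccinia-related conditions.

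**The concern.** The boost was added by amendment to a protocol written around two confined dosing periods. A site reading the general sections and a site reading the boost section would monitor the same subject differently on the dosing day. Section 9.4.3 uses mandatory wording, so every boost, in up to 24 subjects (at most 12 per cohort), either departs from that rule or is run outside the written boost schedule. All boosts are given at 10^8 pfu, so cohort 1 meets that dose for the first time at this visit.

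The ECG conflict decides whether a kind of safety data exists at all. The day-28 recording is the only post-boost ECG named anywhere in the protocol. If it is not made, no analysis can recover it, and ECG findings after the third dose cannot be described.

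**Working it through.** The protocol states no figure for this point and no formula applies. The check sets the provisions side by side and counts scheduled assessments.

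**1. Observation.**

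| Source | Doses 1 and 2 | Dose 3 |
|---|---|---|
| 7.4.1.2 and 9.4.3 | 24 h | 24 h (no exemption) |
| Setting (9.4.10.3.1; 9.4.10.3.5) | Confinement, discharge not before 24 h | Ambulatory visit, no discharge time |
| Timed post-dose checks (9.4.10.3.3 and Table 2a; 9.4.10.3.5 and detailed third-dose table) | 2, 4, 6, 8, 12, 24 h = 6 | 2, 4, 6 h = 3, then a day-1 visit |
| Days with a ± 30-minute vital-sign window (9.5.2.5) | 0, 1, 28, 29 | 0 only |

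For doses 1 and 2 the general rule and the schedule agree. For dose 3 nothing in the schedule delivers 24 hours under observation by the study team. The last timed staff contact on day 0 is at 6 h, and the next is a day-1 visit with no stated hour.

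The schedule footnote does not settle this: "Subjects will be monitored and evaluated for AEs for at least 30 minutes after vaccination in attendance of an investigator". It is attached to all three dosing days, and section 7.4.1.2 has the same sentence directly after its 24-hour requirement. It sets the minimum time with an investigator present and does not replace the 24 hours.

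**2. ECG.**

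| After | Scheduled ECGs | Count |
|---|---|---|
| Dose 1 | Days 7 and 14 (also day 28, the day of dose 2) | 2 (3 with day 28) |
| Dose 2 | Days 35 and 42 | 2 |
| Dose 3, text of 9.4.10.3.6 | Day 28 post-boost | 1 |
| Dose 3, boost schedule table | None (the only tick is pre-dose) | 0 |

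Across the extension this is at most 24 × 1 = 24 post-boost ECGs by the text and 24 × 0 = 0 by the table. Section 9.5.2.4 sends the reader to the schedule table, so following that reference gives 0. The reference itself is loose for the boost phase: it names Table 1, while the boost schedule is headed Table 2b, a label it shares with the detailed third-vaccination table.

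**3. Effect on reactogenicity data.** Staff contacts in the first 24 hours are 6 after doses 1 and 2, and 3 + 1 = 4 after dose 3 if the day-1 visit is counted. The missing ones are at 8 h and 12 h. Staff-assessed days within the 14-day window are:

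- Dose 1: days 0, 1, 3, 7, 14 = 5
- Dose 2: days 28, 29, 35, 42 = 4
- Dose 3: days 0, 1, 3, 7, 14 = 5

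The daily diary runs for 14 days after each dosing (9.5.2.8.9). The imbalance is therefore confined to the hours between 6 h and the day-1 visit.

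**The case against.** **On observation.** The ambulatory design of the boost is consistent across the text, the schedule and the detailed table, so the general 24-hour sentences could be wording that the extension left untouched. The log for amendment 03 lists section 9.4.10.3.5 among the changes but neither 7.4.1.2 nor 9.4.3. That may explain how the conflict arose, but it does not remove it: both rules are in force as written and the documents do not rank them. It is also fair that a visit ending at 6 h is only an inference, since no discharge time is given. The contradiction does not depend on it, because no overnight stay is written either.

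**On cardiac safety.** Troponin T is scheduled on the boost dosing day and at day 28 in both text and table, so some post-boost cardiac data are planned under either version. Myo-/pericarditis is one of several potential risks named. Both points stand and limit the issue to the ECG.

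**Stronger readings that the documents do not support.** A reader might infer that dose-3 reactogenicity cannot be compared with doses 1 and 2. The endpoint is occurrence over 14 days, the diary covers 14 days after every dose, and dose 3 has as many staff-assessed days as dose 1 and one more than dose 2. Only the 8 h and 12 h checks differ, and the direction of any effect is unknown.

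A reader might also take section 9.5.3.5.4, "The results of the 12 lead ECG will be listed by sampling times (screening and follow up"), to leave the ECGs of days 7, 14, 28, 35 and 42 out of the report. That requires follow-up to mean the day-180 visit alone. Table 1a has no ECG on that day, so the phrase would then be empty for the two-dose schedule. Sections 9.5.3.5 and 9.8.1.3 also provide for review and listing of individual values. The wording is loose, but no recording is shown to be lost.

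**Conclusion.** The point holds as two internal contradictions in the third-dose monitoring: a 24-hour observation rule with no exemption against an ambulatory visit whose last timed dosing-day check is at 6 h, and a day-28 post-boost ECG present in the text (1 per subject) but absent from the boost table (0 per subject). The second determines whether any post-boost ECG is recorded. The text and the detailed table agree on the 2, 4 and 6 h checks, so that finding does not rest on one table. The ECG count assumes that the boost schedule's ECG row was read correctly: it holds a single tick, marked as pre-dose, so a shifted column could not supply a second recording. It also takes the Table 1 reference in 9.5.2.4 to extend to the boost schedule.

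The consequence for reactogenicity is small: a difference in first-day capture, to be stated when reactions are described by injection. No sample size, power or error rate is affected, since the protocol plans no confirmatory test.

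**What to change.** - Reconcile sections 7.4.1.2 and 9.4.3 with section 9.4.10.3.5 and the detailed third-vaccination table, so that one observation rule applies to the third dose and every place states it. Which rule that is remains a clinical decision for the sponsor and investigator.
- Reconcile the day-28 list in section 9.4.10.3.6 with the boost schedule table, so that the ECG is either in both or in neither. Give the boost schedule its own table number and make section 9.5.2.4 refer to it.
- Where adverse events are tabulated by dose level and injection (9.5.3.5.1), add a note that the 8 h and 12 h staff checks were made after doses 1 and 2 only.

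The cost is amendment wording and one table note. No procedure is needed beyond those the protocol already names, although site workload will depend on which rule is kept. The reconciliation should precede the boosts, because an ECG that was not recorded cannot be obtained later.
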